1.4 STUDY RATIONALE

Standard treatment for subjects with chronic lymphocytic leukemia (CLL) is rapidly evolving and gradually has incorporated the use of monoclonal antibodies and targeted therapy with small molecules. Based on the data from the CLL-11 study (Goede et al., 2014), GA101 - Obinutuzumab was approved in 2013 for front line treatment of CLL subjects. In addition, Ibrutinib has been recently approved in February 2014 by the FDA, as a single agent for treatment of subjects with relapse refractory CLL. There is no data available testing the combination of Ibrutinib with GA101 – Obinutuzumab, but their separate mechanism of action and non-overlapping adverse events makes them ideal for administration together with an expected synergistic effect.

The CLL-11 study demonstrated that GA101 – Obinutuzumab in combination with Chlorambucil induce higher overall and complete responses, and conferred a statistically significant benefit in terms of progression free and overall survival compared to subjects receiving single agent chlorambucil. These data provided the support for the FDA approval on November 1, 2013. This and other studies using chlorambucil combination strategies (Hillmen et al., 2013) have shown that the benefit of adding chlorambucil to these combination regimens is questionable and it is likely that, instead of providing additive or synergistic interaction, it may increase the rate of adverse events including cytopenias and infections. Similarly, single agent Ibrutinib has shown to be

Ibrutinib + GA101 – Obinutuzumab. University of California, San Diego

effective in previously untreated subjects including those that are older than 65 or considered unfit to receive chemotherapy based combinations (O'Brien et al., 2014). The response rate (Overall response of 71% and complete response of 13%) could be higher in subjects receiving Ibrutinib but the mobilization of lymphocytes, which is typically asymptomatic, decreases the response rate due to lack of complete fulfillment of IWCLL criteria. Ibrutinib-induced lymphocytosis could be ameliorated by using a monoclonal antibody therapy as shown by Burger et al. In this study, when Ibrutinib was administrated in combination with Rituximab, lymphocytosis resolved more rapidly and completely, and consequently the overall response rate was higher (90-95%) (Burger et al., 2013).

There is no data available assessing the combination of Ibrutinib with GA101 – Obinutuzumab in the elderly population (\geq 65 years old) or in those subjects < 65 years of age where the chemotherapy based agents is contraindicated. We hypothesize that Ibrutinib in combination with GA101 – Obinutuzumab will be well tolerated and will induce higher response rates than the response rate observed in the CLL11 Study (Goede et al., 2014).

2. OBJECTIVES

2.1 PRIMARY

- Primary Objective Phase IB:
 - To evaluate the safety, tolerability and dose limiting toxicity (DLT) of Ibrutinib in combination with GA101 - Obinutuzumab in previously untreated CLL subjects.
- Primary objective Phase II:
 - To determine the overall response rate (partial response + complete response rate) of Ibrutinib in combination with GA101 - Obinutuzumab in previously untreated subjects with CLL.

2.2 SECONDARY

- To determine progression-free survival (PFS), treatment-free survival (TFS) and overall survival (OS) in previously untreated CLL subjects that will receive treatment with Ibrutinib in combination with GA101 Obinutuzumab.
- To determine the percentage of previously untreated CLL subjects treated with Ibrutinib plus GA101 Obinutuzumab that achieve negative minimal residual disease (MRD^{neg}) in the bone marrow or peripheral blood using multiparameter flow cytometry (4 colors).

Ibrutinib + GA101 - Obinutuzumab. University of California, San Diego

• To evaluate correlative studies in samples collected from previously untreated CLL subjects treated with Ibrutinib / GA101 – Obinutuzumab combination regimen including but not limited to the following: assessment of the chemokine and cytokine profile using plasma samples from the subjects and correlation of the results with the presence of Infusion-Related Reactions (IRRs).

3. STUDY DESIGN

3.1 DESCRIPTION OF THE STUDY

This is an open label phase IB/II clinical trial to determine the safety, tolerability and clinical activity of Ibrutinib in combination with GA101 - Obinutuzumab. **Pharmacyclics** will provide Ibrutinib during the course of the 6 cycles and after cycle 6, during the following 3 years. GA101 – Obinutuzumab will be requested to be covered by the insurance as a Standard of Care treatment for previously untreated subjects. Phase Ib

We will evaluate safety, tolerability and dose-limiting toxicities (DLTs) during the first cycle of treatment (4 weeks; Day 1-28). The phase IB will be performed as a safety run-in in the first 6 subjects enrolled. The sample size of 6 subjects is considered to be sufficient to support preliminary safety, tolerability and DLTs assessments (Goede et al., 2013). For additional statistical considerations see section 10.2.6.

Subjects will be enrolled at least one week apart to ovoid overlapping time of observation during the first week of treatment when infusion reactions are expected to be higher.

If no more than one of six subjects experiences DLTs, we will proceed to the Phase II described below.

3.1.1 Phase II

In the phase II we will determine response rate in all subjects that have received treatment. This study will enroll 32 subjects and the sample size has been calculated using a Simon two-stage design (Simon, 1989). In the first stage, 10 subjects will be enrolled. If 8 or fewer responses are observed at the end of this stage, then the study will be terminated for futility. If at least 9 responses are observed, an additional 22 subjects will be enrolled in a second stage, for a total of 32 subjects. If at least 29 responses are observed among the 32, then efficacy of the treatment will be concluded. For additional statistical considerations see section 10.3.4.

Response assessments will be evaluated based on the International Workshop in CLL Guidelines (IWCLL) (Hallek et al., 2008).

Ibrutinib + GA101 - Obinutuzumab. University of California, San Diego

The estimated accrual time from first to last subject enrolled in the study will be 24 months (including the safety run-in of the phase lb)

3.2 OUTCOME MEASURES

3.2.1 Phase IB Outcome Measures:

The safety and tolerability of Ibrutinib in combination with GA101 - Obinutuzumab will be assessed using the following primary safety outcome measures:

- Type, Incidence, nature, and severity of AEs.
- The relationship of AEs to Ibrutinib and/or GA101 Obinutuzumab
- Serious adverse events
- Incidence of adverse events leading to Ibrutinib/GA101 Obinutuzumab discontinuation or dose delays.
- Incidence of adverse events of special interest
- Clinical laboratory abnormalities
- Deaths and cause of death
- Dose limiting toxicity (DLT): DLTs will include possibly related or related events that are Grade ≥ 3 that do not resolve to Grade ≤ 1 within 14 days of initiation despite appropriate medical management. Some exceptions will apply (See section 10.2.4).

3.2.2 Phase II Outcome Measures:

Response assessment will be performed by physical examination, CT scan evaluation and bone marrow biopsy/aspirate at completion of therapy using the International Workshop in CLL Guidelines (IWCLL) (Hallek et al., 2008).

• Primary:

- Overall response rate (ORR): defined as the proportion of subjects who achieve complete response (CR), complete response with incomplete marrow recovery (CRi), nodular partial response (nPR), or partial response (PR) per IWCLL 2008 criteria over the course of the study.
- Progression Free Survival (PFS): Time measured from initiation of therapy until clinical or laboratory evidence of CLL progression.
- Treatment Free Survival (TFS): Time measured from initiation of therapy until next treatment for CLL.
- Overall Survival (OS): Time measured from initiation of therapy until death from any cause.

• Secondary:

Ibrutinib + GA101 - Obinutuzumab. University of California, San Diego

- Rate of MRD^{neg} CRs in the bone marrow or peripheral blood using multiparameter flow cytometry (4 colors).
- Clinical, laboratory and radiological evidence of response to administration of Ibrutinib plus GA101 Obinutuzumab based in the International Workshop in CLL Guidelines (IWCLL) (Hallek et al., 2008).

4. STUDY POPULATION

Previously untreated CLL subjects ≥ 65 years of age or subjects < 65 years that
refuse to be treated with chemotherapy or that are not candidates for treatment
with chemotherapy agents.

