	criteria for initiation of therapy) (Hallek et al., 2008). The study will include a Screening Phase, a Treatment Phase, and a Follow-up Phase. The Screening Phase assessments will be performed within 28 days prior to treatment. The Treatment Phase will extend from first dose until completion of all planned cycles of treatment (#6) or study drug discontinuation.	

Ibrutinib + GA101 – Obinutuzumab. University of California, San Diego

All subjects will receive Ibrutinib 420 mg (3 x 140-mg capsules) orally once daily for up to 6 cycles. The treatment with Ibrutinib will continue after cycle 6 for the following 3 years until disease progression, unacceptable toxicity or other reason for treatment discontinuation.

All subjects will receive GA101 – Obinutuzumab by IV infusion for up to 6 cycles (28-day cycles) as follow:

- On Cycle 1, Day 1, 100 mg GA101-Obinutuzumab will be administered.
- On Cycle 1, Day 2, 900 mg of GA101-Obinutuzumab will be administered.
- On Cycle 1, Days 8 and 15, 1,000 mg of GA101-Obinutuzumab will be administered.
- On Cycles 2 6, Day 1, 1,000 mg of GA101-Obinutuzumab will be administered.

Subjects will undergo response assessment two months after completion of the study treatment. The initial follow-up evaluations will be made (after the response assessment) every 3 months during 9 months and later every 6 months until initiation of new treatment for CLL, consent withdrawal or death. During the long-term follow-up phase, subjects will be followed for survival (PFS, TFS and OS). The long-term follow-up phase will continue until disease progression, death, loss to follow up, consent withdrawal, or study end, whichever occurs first.

An evaluation of the End of Study will be performed due to initiation of new treatment for CLL or withdrawal of consent.

Population

Males and females with previously untreated chronic lymphocytic leukemia (CLL):

- > 65 years of age, or
- < 65 years that refuse to be treated with

Ibrutinib + GA101 – Obinutuzumab. University of California, San Diego

	chemotherapy or subjects that are not candidates for treatment with chemotherapy agents.	
Center	UCSD Moores Cancer Center	

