Ibrutinib + GA101 - Obinutuzumab. University of California, San Diego

marrow recovery (CRi), nodular partial response (nPR), or partial response (PR) per IWCLL 2008 criteria over the course of the study.

- Progression Free Survival (PFS): Time measured from initiation of therapy until clinical or laboratory evidence of CLL progression.
- *Treatment Free Survival (TFS):* Time measured from initiation of therapy until next treatment for CLL.
- Overall Survival (OS): Time measured from initiation of therapy until death from any cause.

• Secondary outcome measures:

- Rate of MRD^{neg} CRs in the bone marrow or peripheral blood using multiparameter flow cytometry (4 colors).
- Clinical, laboratory and radiological evidence of response to administration of Ibrutinib plus GA101 – Obinutuzumab based in the International Workshop in CLL Guidelines (IWCLL) (Hallek et al., 2008).

1. INTRODUCTION

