9.5 EVALUATION EVERY 6 MONTHS UNTIL PROGRESSION OR WITHDRAWAL FROM THE STUDY

Long-term follow-up will continue every 6 months until initiation of new treatment, consent withdrawal from the study or death, whichever occurs first. These evaluations will include the following

• Physical examination including vital signs, lymph node, spleen and liver measurements, performance status, adverse event assessment, current medications, and recording of transfusion of blood products.

Ibrutinib + GA101 - Obinutuzumab. University of California, San Diego

- Liver chemistries: (ALT, AST, total bilirubin and Alkaline phosphatase)
- CBC with differential, platelet count, complete metabolic panel with uric acid, LDH, albumin, creatinine, BUN, total protein, fasting blood glucose, calcium, sodium, potassium, chloride, phosphorus and HCO3.

Beta-2 microglobulin, quantitative immunoglobulin levels (IgG, IgA, IgM). Continue monitoring of quantitative immunoglobulins (IgG, IgA, and IgM) for up to 2 years after completion of therapy or until they return to baseline.

- Pregnancy monitoring for women of child bearing potential should continue with every follow-up evaluation until 12 months following the last dose of GA101 Obinutuzumab.
- Chest, abdominal and pelvic CT scan or MRI in those subjects with clinical or laboratory alterations that suggest disease progression based on IWCLL criteria.
- For subjects that maintain a CR (based on clinical and hematological assessments), additional CT scans of the chest, abdomen and pelvis will be performed after 3 years of completion of study treatment in order to assess response based on clinic and radiologic parameters, and discuss the possibility of Ibrutinib discontinuation.
- For subjects that maintain a CR (based on clinical and hematological assessments), an additional bone marrow biopsy and aspirate will be performed after 3 years of completion of study treatment in order to assess MRD and discuss the possibility of Ibrutinib discontinuation.

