10.3.2 Efficacy Population

The Efficacy Population includes all subjects who receive at least one dose of study drug and have baseline and at least one post-baseline efficacy assessment.

10.3.3 Efficacy Analysis

Response assessment will be performed by physical examination, CT scan evaluation and bone marrow biopsy/aspirate at completion of therapy using the International Workshop in CLL Guidelines (IWCLL) (Hallek et al., 2008) (See section 3.2.2). The ORR will be estimated with an exact 95% confidence interval (CI) for the combination regimen of Ibrutinib/GA101 – Obinutuzumab.

Median PFS, TFS and OS, and their 95% CI will be estimated using the Kaplan-Meier method.

10.3.4 Statistical Operating Characteristics of the Phase II

The sample size calculation has been made using a comparative overall response with GA101 – Obinutuzumab in combination with chlorambucil, which is a standard of care regimen for previously untreated CLL subjects. This combination regimen can induce an overall response rate (ORR) of 78% in CLL subjects (Goede et al., 2014). For the purpose of our sample calculation we will use a true ORR of 78% that will be tested against an alternative of 94%, which corresponds to the expected ORR that can be achieved when GA101 – Obinutuzumab is administered in combination with lbrutinib.

There is no data available using the combination of Ibrutinib and GA101 - Obinutuzumab, therefore we will use as a point of reference for the expected ORR, the recently published data of Ibrutinib in combination with Rituximab in relapse/refractory CLL subjects. In this publication the ORR was in the 90-95% range (Burger et al., 2013).

Ibrutinib + GA101 - Obinutuzumab. University of California, San Diego

Our sample size calculation will use an ORR endpoint comparison based on the ORR achieved with the Ibrutinib and GA101 - Obinutuzumab combination. We hypothesize that Ibrutinib in combination with GA101 - Obinutuzumab would induce an ORR of 94%, which is 16% higher than the ORR observed in the study published by Goede et al. (Goede et al., 2014)

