10.8 SECONDARY EFFICACY VARIABLES

- PFS, TFS and OS. Clinical parameters that will be measured from initiation of treatment until occurrence of the event.
- MRD measured by multiparameter (4 colors) flow cytometry.

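### PFS and TFS leave out death as an event, so the planned Kaplan-Meier curves estimate time to progression and time to next treatment and sit at or above true PFS and TFS

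*Combined protocol and SAP*

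**What the plan says.** Section 3.2.2 (Phase II Outcome Measures) lists three time-to-event outcomes, and the synopsis repeats them:

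- PFS: "Progression Free Survival (PFS): Time measured from initiation of therapy until clinical or laboratory evidence of CLL progression".
- TFS: "Time measured from initiation of therapy until next treatment for CLL".
- OS: "Time measured from initiation of therapy until death from any cause".

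Section 10.3.3 gives the analysis: "Median PFS, TFS and OS, and their 95% CI will be estimated using the Kaplan-Meier method". Section 10.8 adds only "PFS, TFS and OS. Clinical parameters that will be measured from initiation of treatment until occurrence of the event", and does not say what the event is. Neither section brings death into PFS or TFS, states a censoring rule, or plans a competing-risk method.

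Death ends follow-up. Section 9.5 reads "Long-term follow-up will continue every 6 months until initiation of new treatment, consent withdrawal from the study or death, whichever occurs first". The Study Design part of the synopsis reads "The long-term follow-up phase will continue until disease progression, death, loss to follow up, consent withdrawal, or study end, whichever occurs first".

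**The concern.** PFS and TFS as named imply that a subject who has died is no longer progression-free or treatment-free and alive. As defined here, such a death is not an event. Because follow-up stops at death, the subject can only be censored.

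Kaplan-Meier assumes that a censored subject could still have the event later, at the same rate as those who remain under observation. That does not hold for a subject who has died. Each death without progression (or without retreatment) therefore holds the PFS (or TFS) curve too high.

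Such deaths are plausible in this population, who are 65 or older, or younger and either unfit for chemotherapy or refusing it. In a single-arm study of 32 subjects, PFS and TFS will be read against other trials, so the definitions need to match the names. The protocol's own account of a cited Phase 3 ibrutinib trial with a PFS primary endpoint (Section 1.2.3.1) counts both progression and death as events.

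**Working it through.** The plan states no event count, rate or precision for PFS or TFS, so there is no figure of its own to reproduce. The check has four parts.

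**1. Direction.** Let p be the yearly hazard of progression and d the yearly hazard of death without progression, both taken as constant and independent.

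- Curve as written: exp(-p·t)
- PFS with death counted: exp(-(p+d)·t)
- Overstatement: exp(-p·t) - exp(-(p+d)·t) = exp(-p·t)·(1 - exp(-d·t))

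This is zero when d = 0 and positive otherwise. It grows with d and shrinks with p. The same formula serves TFS with the hazard of next treatment in place of p. The documents give no retreatment rate, so no separate TFS figure is offered.

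**2. Size over an assumed range** (p = 0.02 to 0.10, d = 0.02 to 0.06 per year; assumptions, not document figures).

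| Time | p, d | As written | Death counted | Gap (points) |
|---|---|---|---|---|
| 2 years | 0.10, 0.02 | 81.9% | 78.7% | 3.2 |
| 2 years | 0.02, 0.06 | 96.1% | 85.2% | 10.9 |
| 3 years | 0.10, 0.02 | 74.1% | 69.8% | 4.3 |
| 3 years | 0.02, 0.06 | 94.2% | 78.7% | 15.5 |

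Expected deaths without progression by 2 years among 32 subjects are 32·d/(p+d)·(1 - exp(-2(p+d))). This gives 1.1 (p = 0.10, d = 0.02) to 3.6 (p = 0.02, d = 0.06). Simulated Kaplan-Meier estimates at 2 years (n = 32, 4,000 runs, censoring at 3.46 years) gave the same 3.2 and 10.9 points.

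A small worked data set shows the mechanism. Take 32 subjects with progressions at months 10 and 26, deaths without progression at months 6, 14, 20 and 30, and 26 subjects event-free at month 36. As written, the 36-month estimate is (30/31)·(27/28) = 93.3%. With death counted it is 26/32 = 81.3%.

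**3. Reference points in Section 1.2.3.1.**

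- *Treatment-naive ibrutinib study.* It reports 93% PFS at 12 months in the 420 mg cohort and no deaths. Then p = -ln(0.93) = 0.0726 per year. At 2 years the curve as written is 86.5%, against 83.1% (d = 0.02) to 76.7% (d = 0.06). Taking median follow-up as the mean, exposure is 26·10.7/12 + 5·4.6/12 = 25.1 patient-years. With no deaths, the one-sided 95% upper bound is 3.0/25.1 = 0.119 per year, so about 12% per year cannot be excluded.
- *Ibrutinib plus rituximab study.* Of 40 subjects at a median of 14 months, 4 had died and 1 had come off study for progression. Counting death raises PFS-type events from 1 to 5. With 40·14/12 = 46.7 patient-years, p = 1/46.7 = 0.021 and d = 4/46.7 = 0.086. The 2-year reading is 95.8% as written against 80.7% with death counted. Those subjects were high-risk with a median of 2 prior therapies, so this is context, not a forecast.

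**4. Medians.** Within the assumed range the shortest median is ln 2/0.16 = 4.3 years with death counted and ln 2/0.10 = 6.9 years as defined now. Section 7 gives six 28-day cycles plus three years, about 3.46 years. The medians would probably not be reached in that time under either definition.

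**The case against.** The strongest case against is that little depends on these endpoints. PFS, TFS and OS are secondary in Sections 2.2 and 10.8, no test or stopping rule uses them, and deaths are reported through OS. The plan names medians, not 2- or 3-year rates, and the medians would probably not be reached. That deaths would be censored is an inference, since no rule is written. The hazards are assumed, and the one ibrutinib plus anti-CD20 study described points to a death rate outside the assumed range.

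Much of this is fair and limits the size of the point. The primary analysis is untouched, and what changes is the curves, any time-point rates and the event counts. The median statement holds only within the assumed range: at p = 0.10 and d = 0.12 the median with death counted is ln 2/0.22 = 3.15 years. Section 9.5 also allows follow-up beyond 3.46 years. The rituximab-combination figures suggest that the assumed death range is not inflated.

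The objection does not rescue the definitions. Read literally, they leave censoring as the only way to handle a death without the event, and the missing rule is part of the same defect.

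Two further objections stand and are carried into the fix. Renaming the endpoints while keeping ordinary Kaplan-Meier would still treat the dead as able to progress. And the synopsis sentence that stops long-term follow-up at progression conflicts with Sections 7 and 9.5, which matters for TFS.

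**Conclusion.** The concern holds. This is a definition that gives the wrong quantity if followed, not merely missing detail. The curves estimate time to progression and time to next treatment. They coincide with PFS and TFS until the first death without the event and lie above them afterwards.

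The direction follows from the definitions. The size rests on assumed constant hazards: 3.2 to 10.9 points at 2 years and 4.3 to 15.5 at 3 years, with zero as the lower limit if nobody dies without the event. For TFS the documents do not address death either way; the problem there is a survival label on a time-to-next-treatment endpoint. The definitions should be corrected, but the response-rate endpoint, the sample size of 32 and the two-stage decision do not depend on them.

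**What to change.** In Section 3.2.2 and the synopsis, and by reference in Sections 10.3.3 and 10.8:

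- Define PFS as time from first dose to IWCLL progression or death from any cause, whichever is first.
- Define TFS as time from first dose to next CLL treatment or death from any cause, whichever is first.
- Censor subjects without an event at their last assessment.

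Alternatively, keep the present definitions, rename the endpoints time to progression and time to next treatment, and report cumulative incidence with death as a competing risk.

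Reconcile the synopsis sentence that ends long-term follow-up at progression with Sections 7 and 9.5, so that deaths between progression and next treatment are captured for TFS.

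Two separate wording points can be settled in the same edit. Cross-refer the progression definition to Section 1.2.4.10, under which treatment-related lymphocytosis alone is not progression. List PFS, TFS and OS as secondary in Section 3.2.2 and the synopsis outcome list, to agree with Sections 2.2 and 10.8.

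The cost is wording only. Under Sections 7 and 9.5, deaths before progression or next treatment already fall within planned follow-up, and OS needs them anyway. If such deaths occur, reported PFS and TFS will be somewhat less favourable.
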